
	
retrospective study] that doesn't affect this study's efficacy and safety as determined by the investigator.)
 
[Laboratory tests]
 
12) At screening, those who had
 
 ① serum alanine aminotransferase (ALT), aspartate aminotransferase (AST), or total bilirubin levels ≥ 2 X upper limit of normal ② serum creatinine or BUN ≥ 2 X upper limit of normal 
[Others]
 
13) Pregnant or breast-feeding women
 
14) Those who do not consent to use appropriate contraceptive methods during the study.
 
 - Appropriate contraceptive methods for patients or their partners - For Male subject: to use barrier method such as male condom and surgical sterilization such as vasectomy - For Female subject: to use 1) hormonal contraceptive such as Intrauterine system : intrauterine hormone-containing system, implant, injection, contraceptive pills, or 2) non hormonal contraceptive such as Intrauterine system : copper loop, barrier method : female condom, diaphragm or cervical cap, or surgical sterilization : tubectomy. 
15) In the opinion of the investigator, those who were unsuitable for any reason.

Investigational product and mode of administration	
[Investigational Product]
 
 ● Study drug: Fexuprazan tablet 40 mg ● Control drug: Esomeprazole capsule 40 mg 
[Treatment period]
 
 ● Treatment 1: 4 weeks A dose of Study drug or Control drug will be administered orally once daily without regard to meals for 4 weeks. The timing of administration should be kept consistent for each subject. ● Treatment 2: Up to 8 weeks (4 weeks + 4 weeks) Patients who have not been healed after the Treatment 1 of investigational product administration will have an additional 4-weeks of treatment period (Treatment 2) with the same mode of administration. Patients that categorized as a non-healed are those with a GERD-Q score >8.

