- 8) Pregnancy test will be performed with serum or urine pregnancy test will be performed at Visit 1. (Women who medically do not have child-bearing potential are exempt from the pregnancy test). If Visit 1 and Visit 2 are conducted on the same day, another pregnancy test (serum or urine test) should be conducted prior to IP administration even if the test result within 2 weeks before the date is available.
- 9) Eligibility of subjects will be assessed based on the results from Visit 2 (However GERD-Q result from Visit 1 will be used as the eligibility criteria).
- 10) Subjects who have not symptoms relief at Visit 4 will be prescribed the investigational product for treatment 2, and subject diary will be distributed to them. At Visit 5, treatment compliance will be checked, and subject diary will be collected only from those who have undergone Treatment 2.
(#: Subject diary completion will be checked at Visit 3, and appropriate training on diary keeping will be performed on the phone, if necessary.)
- 11) The Safety F/U will be conducted as a telephone visit within 2 weeks (\pm 5 days) from Last day of Visit 4 and Visit 5 only in subjects who complete all protocol-specific treatments, and the subjects may visit for additional tests or treatments based on the investigator's judgment.
- 12) If a subject decides to discontinue participation or is withdrawn from the study before completion, the Withdrawal visit procedures will take place within 2 weeks from the withdrawal decision. At the Withdrawal visit, the unused IPs or empty packaging will be returned, and the subject diary will be collected. However, assessment of Gastroesophageal Reflux Disease Questionnaire (GERD-Q)^{*)} and quality of life questionnaire (GERD-HRQL)^{*)} must be performed. If the patient refused to visit, above two Questionnaires can be done by telephone call and the document should be written on the EMR by the investigator.
- 13) Subjects who have not been healed after the Treatment 1 of investigational product administration will have an additional 4-weeks of treatment period (Treatment 2) with the same mode of administration.

[Abbreviations and Definition of Terms]

ADR	Adverse drug reaction
AE	Adverse event
AIDS	Acquired immune deficiency syndrome
ALT	Alanine aminotransferase, alanine
ANCOVA	Analysis of Covariance
APA	Acid pump antagonist
AST	Aspartate transaminase, aspartate
ATC	Anatomical therapeutic chemical
BUN	Blood urea nitrogen
BPOM	Indonesia Food and Drug Authority

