8.4.1.2 Secondary Efficacy Endpoints

1. Proportions of subjects with symptoms relief at week 8 measured by GERD-Q Score <8
(Week 8 evaluation will only be applicable to patient receiving treatment 2)

2. Assessment on symptoms based on the diary of subjects

- The day to reach complete response (disappearance of heartburn, acid regurgitation, or heartburn/acid regurgitation for 7 consecutive days) after the first IP administration.
- Proportions of subjects without the major symptoms (heartburn, acid regurgitation, or heartburn/acid regurgitation) for first 7 days, 4 weeks, and 8 weeks after the first IP administration.
- Proportions of days free of major symptoms (heartburn, acid regurgitation, or heartburn/acid regurgitation) for first 7 days, 4 weeks, and 8 weeks after the first IP administration (including all daytime, nighttime, and daytime/nighttime)
- However, the secondary efficacy endpoints will only be assessed in patients who are not healed with treatment 1 and will continue to receive safety and rescue.

(Week 8 evaluation will only be applicable to patient receiving treatment 2)

3. Assessment on symptoms of reflux disease (GERD-Q)

- Changes from baseline in frequency by major symptom after 7 days, 4 weeks and 8 weeks.
(Week 8 evaluation will only be applicable to patient receiving treatment 2)

4. Assessment of Quality of Life (GERD-HRQL: GERD-Health related quality life)

- Changes from baseline in the total score of GERD-HRQL after 7 days, 4 weeks and 8 weeks.
(Week 8 evaluation will only be applicable to patient receiving treatment 2)

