9.2.3.2 Secondary Efficacy Assessment

1. Proportions of subjects with symptoms relief at week 8 measured by GERD-Q Score <8

The proportions of subjects with symptoms relief by Week 8 and their 95% confidence intervals will be provided by group. The proportions of subjects with symptoms relief by Week 8 will be calculated as the cumulative symptoms relief by using the results at the time of final observation including the Withdrawal visit. To compare the control group and study group, the lower bound of the 2-sided 95% confidence intervals will be obtained by using the Chi Square test or Fisher's Exact test method. If this lower bound is greater than the non-inferiority margin of -0.1, the study group will be judged to be non-inferior to the control group. (Week 8 evaluation will only be applicable to patient receiving treatment 2)

2. Assessment on symptoms based on the diary of subjects

- CR (disappearance of heartburn, acid regurgitation, or heartburn/acid regurgitation for 7 consecutive days) is defined as the symptom score of 0 for 7 consecutive days for the first time after the first dose, and the survival time is defined as the time to reach Complete Response (CR) after the first IP administration. Kaplan-Meier plots will be drawn by treatment group, and the medians and their 2-sided 95% confidence intervals will be presented. To compare the control group and study group, the log-rank test will be used.
- The number of subjects without any heartburn, acid regurgitation, or heartburn/acid regurgitation for the first 7 days, full 4 weeks, and full 8 weeks from the first IP administration, the proportion (%) of these subjects and its 95% confidence interval will be presented by treatment group. To compare the control group and study group, the 2-sided 95% confidence intervals and p-value will be obtained by using the Chi Square test or Fisher's Exact test method.

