Descriptive statistics (mean, standard deviation, median, minimum, and maximum) for the changes from baseline in the total score of quality of life at the first 7 days, 4 weeks, and 8 weeks will be presented by time point. For the changes from baseline in variables measured at the first 7 days, 4 weeks, and 8 weeks after the IP administration, an ANCOVA model including treatment group as treatment effect, baseline values, and stratification factor (based on dominant symptoms in inclusion criteria: experiencing heartburn, regurgitation, or both of them more than >3 days in the last 7 days) as covariate will be applied. The results of ANCOVA model will be summarized as the least squares mean (LSM) and standard error by treatment group, the LSM differences between the study group and the control group, the corresponding 2-sided 95% confidence interval, and p-value. (Week 8 evaluation will only be applicable to patient receiving treatment 2)

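### The Week 8 relief test has two possible denominators, and the same data can pass the -0.1 margin on one and fail it on the other

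*Combined protocol and SAP*

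**What the plan says.** For Week 8 relief, section 9.2.3.2 (item 1) and the matching synopsis paragraph state: "The proportions of subjects with symptoms relief by Week 8 will be calculated as the cumulative symptoms relief", taken at the final observation including the Withdrawal visit. For the comparison, "the lower bound of the 2-sided 95% confidence intervals will be obtained by using the Chi Square test or Fisher's Exact test method", and the decision rule is "If this lower bound is greater than the non-inferiority margin of -0.1, the study group will be judged" non-inferior. The same paragraph ends with "Week 8 evaluation will only be applicable to patient receiving treatment 2".

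The note recurs after the Week 8 diary, GERD-Q and GERD-HRQL analyses and the exploratory proportions (synopsis, sections 9.2.3.2 and 9.2.3.3), all of which carry between-arm p-values. The GERD-HRQL analysis is "an ANCOVA model including treatment group as treatment effect, baseline values, and stratification factor".

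A bullet under the diary item in section 8.4.1.2 goes further: "However, the secondary efficacy endpoints will only be assessed in patients who are not healed with treatment 1".

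Entry to Treatment 2 is described in two ways. The synopsis (treatment period) says "Patients that categorized as a non-healed are those with a GERD-Q score >8". Footnote 10 of the activity schedule says "Subjects who have not symptoms relief at Visit 4 will be prescribed the investigational product for treatment 2", and section 8.4.2.1 defines relief as a GERD-Q score below 8. Sections 5.1, 8.1 and 8.3.14 also tie healing or Treatment 2 to relief.

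**The concern.** Subjects relieved at Week 4 leave after a safety follow-up (sections 5.1 and 8.1) and have no Visit 5. They are either Week 8 successes carried forward or outside the Week 8 denominator, and the plan does not say which. Section 9.1 defines no Treatment 2 set, and section 8.4.2.1 describes the calculation for Week 4 only.

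On the restricted reading, the groups are formed by a post-randomization outcome that treatment itself affects. A difference between them does not estimate a treatment effect protected by randomization, and a -0.1 margin cannot be met reliably with so few subjects. The study is open label, so a denominator chosen once results are visible would be hard to defend.

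Taken literally, the bullet in section 8.4.1.2 would also confine the 7-day, 4-week and time-to-complete-response endpoints to Week 4 failures. Elsewhere only Week 8 is restricted. Subset membership is itself unclear: a GERD-Q score of exactly 8 is neither relieved (below 8) nor non-healed (above 8).

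**Working it through.** **Inputs.** From section 9.4.2: Week 4 relief 94.0% (study) and 88.5% (control), margin -0.1, one-sided alpha 2.5%, 53 per group, 20% dropout, 134 in total. The documents give no Week 8 relief rate, so the Week 8 values below are assumptions.

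**1. The plan's own figure.** Power = Φ[(0.055 + 0.10 − 1.96 × SE pooled) / SE unpooled].
- The mean rate is 0.9125, so SE pooled = √(2 × 0.9125 × 0.0875 / 53) = 0.0549.
- SE unpooled = √[(0.94 × 0.06 + 0.885 × 0.115) / 53] = 0.0546.
- Power is 0.80729, as printed; n = 52 gives 0.79984. Then 53 / 0.8 = 66.25, so 67 per arm and 134 in total.

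The plan gives no power for Week 8.

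**2. Size of the Treatment 2 subset at the planning rates.**
- 53 per arm: 53 × 0.06 = 3.2 against 53 × 0.115 = 6.1.
- 67 per arm: 67 × 0.06 = 4.0 against 67 × 0.115 = 7.7.

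The subset is smaller if a score above 8 governs entry.

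**3. Same data, two denominators.** The plan names no interval formula for the difference, so two are shown, with d = pT − pC.
- Wald: L = d − 1.96 × √[pT(1 − pT)/nT + pC(1 − pC)/nC].
- Newcombe: L = d − √[(pT − lT)² + (uC − pC)²], where l and u are Wilson limits.

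Example, 2/3 vs 4/6. Wald: 0 − 1.96 × √(0.2222/3 + 0.2222/6) = −0.653. Newcombe: 0 − √[(0.667 − 0.208)² + (0.903 − 0.667)²] = −0.516.

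| Illustration | Denominator | Relief | Newcombe | Wald | Against -0.1 |
|---|---|---|---|---|---|
| 53 per arm | Treatment 2 only | 2/3 vs 4/6 | -0.516 | -0.653 | fails |
| 53 per arm | All subjects | 52/53 vs 51/53 | -0.066 | -0.044 | passes |
| 67 per arm | Treatment 2 only | 3/4 vs 6/8 | -0.484 | -0.520 | fails |
| 67 per arm | All subjects | 66/67 vs 65/67 | -0.053 | -0.035 | passes |

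Miettinen-Nurminen bounds (-0.599, -0.066, -0.540, -0.053) give the same verdicts. With 3 vs 6 entrants there are 4 × 7 = 28 possible Treatment 2 outcomes. By Newcombe, 18 pass cumulatively and fail in the subset, 4 pass both and 6 fail both.

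**4. Chance of meeting -0.1.** Assumed cumulative Week 8 relief, study/control: 97/96, 98/96 and 98/95%. The implied Treatment 2 relief is (cumulative − Week 4) / (1 − Week 4):
- Study: (0.97 − 0.94)/0.06 = 50.0% or (0.98 − 0.94)/0.06 = 66.7%.
- Control: (0.96 − 0.885)/0.115 = 65.2% or (0.95 − 0.885)/0.115 = 56.5%.
- Subset differences: -15.2, +1.4 and +10.1 points, so even the direction is not known.

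Exact enumeration, with binomial subset sizes and an empty arm counted as not met, in the order of the three pairs:

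| Denominator | n per arm | Newcombe | Wald |
|---|---|---|---|
| All subjects | 53 | 0.716, 0.850, 0.882 | 0.878, 0.954, 0.964 |
| All subjects | 67 | 0.825, 0.924, 0.949 | 0.937, 0.983, 0.988 |
| Treatment 2 only | 53 | 0.020, 0.048, 0.089 | 0.135, 0.248, 0.285 |
| Treatment 2 only | 67 | 0.019, 0.053, 0.102 | 0.107, 0.226, 0.263 |

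Of the Wald subset passes, 1 to 4 points come from zero-width intervals, where each arm is at 0% or 100%.

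**5. A different assumption.** With equal Treatment 2 relief in both arms, anywhere from 30% to 90%, simulation (Newcombe) has the cumulative reading pass while the subset fails in 70-96% of trials (53 per arm) or 80-96% (67 per arm).

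**6. Week 8 GERD-HRQL model.** Taking one baseline term and a three-level symptom factor, the parameters are intercept + treatment + baseline + 2 = 5. That leaves 9 − 5 = 4 to 12 − 5 = 7 residual degrees of freedom.

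**The case against.** The text leans toward the cumulative reading. The Week 8 paragraph repeats the wording of the Week 4 primary analysis, and the word cumulative does almost nothing in a group made up only of Week 4 failures. A Week 4 reliever's final GERD-Q observation is Visit 4, and section 9.2.1 names only the PPS and FAS for efficacy. This is fair, and it is why the fix adopts that reading. It does not settle the matter, because the note and the bullet in section 8.4.1.2 point the other way.

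The harm is also mostly in one direction. At the planning rates and assumed pairs, the subset passes while the cumulative test fails with probability at most 0.011% (Newcombe) or 0.10% (Wald). The main risk is therefore a lost secondary claim and not a false one. The reverse can occur away from those rates. With Week 4 relief of 40/53 vs 50/53 and Treatment 2 relief of 8/13 vs 0/3, the cumulative bound is -0.152 (fails) and the subset bound -0.003 (passes), by Newcombe.

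The Wald subset range depends on the assumed rates. At 90% relief in both arms it rises to about 50%, of which 30 to 37 points come from zero-width intervals. The Newcombe figure there is below 1%, so the conclusion stands, but 11-29% should not be read as general.

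Finally, labelling the Week 8 subset tests exploratory, rather than dropping them, would be a defensible alternative.

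**Conclusion.** The concern holds. The Week 8 denominator is not defined, and its choice can decide the non-inferiority verdict. At the planning rates the restricted reading rests on about 9 to 12 non-randomized subjects. Its chance of meeting -0.1 is 2-10% (Newcombe) or 11-29% (Wald), against 72-95% or 88-99% over all subjects. These ranges rest on the three assumed pairs of Week 8 rates and on 53 to 67 per arm. The illustrated bounds in step 3 give the same verdicts under all three interval methods tried. The endpoint is secondary, and the Week 4 primary test and the sample size are unaffected. It should be fixed before analysis.

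**What to change.** 1. Define the Week 8 endpoint as cumulative relief by Week 8 over all FAS/PPS subjects, counting Week 4 relief as relief and using Visit 5 or the last observation for the others. Apply -0.1 only there. Label it cumulative, not sustained, relief, and reword the note so that it says only who attends Visit 5.
2. Report Week 8 results in Treatment 2 subjects (diary, GERD-Q, GERD-HRQL, exploratory) descriptively by arm, with no between-arm test or non-inferiority claim. State whether the LOCF rule in section 9.2.1 carries Week 4 relievers' GERD-Q values to Week 8.
3. Reconcile the bullet in section 8.4.1.2 with the synopsis and section 9.2.3.2, so that the 7-day, 4-week and time-to-complete-response endpoints use all FAS/PPS subjects. Its wording on safety and rescue is for the sponsor to reconcile.
4. Reconcile the synopsis definition of non-healed with sections 5.1, 8.1, 8.3.14 and 8.4.2.1 and schedule footnote 10 for a score of exactly 8. This review does not propose which rule applies.

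**Cost.** Wording changes to the synopsis and sections 8.4.1.2, 8.4.1.3, 9.2.3.2 and 9.2.3.3, plus whichever entry-rule text the sponsor changes. Section 11.10 requires IRB approval and, once the study has started, limits amendments to exceptional cases. Items 1 to 3 need no extra subjects or visits. The drawback is that Week 4 relievers have no Week 8 GERD-Q, so the measure cannot show that relief lasted.

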5.1 Scheduled Completion

If all protocol-specified procedures and assessments are completed after the IP administration, the subject will be considered to have completed the study. Subjects with symptoms relief at Week 4 measured by GERD-Q Score <8 will have the Safety F/U after 2 weeks from the date and be terminated from the study.

In this study, completion of the last subject is defined as the end of study.

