8.3.14 Distribution and Collection of Subject Diary

The subject diary will be distributed at Visit 2 and the training on how to complete it will be provided. The completion status of the subject diary will be checked at Visit 3 via site visit, and appropriate training on the diary keeping will be performed, if necessary. At Visit 4, the completed subject diary will be collected and the subjects who have not symptoms relief will be prescribed the IP for Treatment 2 and the subject diary will be re-distributed to the subject. At Visit 5, the subject diary will be collected only from those who have undergone Treatment 2. Assessment of symptoms and treatment compliance will be done based on the subject diary

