9.2 Statistical Analysis Method

9.2.1 General Principles of Result Analysis

The efficacy analysis will be conducted primarily on the PPS and FAS, and the PPS will be the primary analysis set.

In principle, all statistical analyses will use SAS® version 9.4 or higher and be performed with a two-sided test at a significance level of 5%, unless otherwise specified.

Descriptive statistics (mean, standard deviation, median, minimum, and maximum) will be calculated and provided for continuous variables, and the frequency and percentage will be provided for categorical variables.

The last observation carried forward (LOCF) method will be applied for correction of missing data of continuous endpoints among efficacy endpoints, and if the LOCF method cannot be applied, the raw data will be analyzed without correcting the missing data. However, the quality-of-life score (GERD-HRQL) will be analyzed using the raw data without applying the LOCF. For survival analysis, censoring will be utilized. When applying the LOCF, if the value immediately before the missing value is the baseline value, it will not be replaced.

The missing values of efficacy endpoints will be handled for both analyses on the FAS and PPS, and the safety endpoints will be analyzed with the raw data without replacing the missing values.

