- Descriptive statistics (mean, standard deviation, median, minimum, and maximum) of the proportions of days free of any heartburn, acid regurgitation, or heartburn/acid regurgitation for the first 7 days, full 4 weeks, and full 8 weeks from the first IP administration will be presented for daytime, nighttime, and daytime/nighttime by group. For comparison between treatment groups, an ANCOVA model will be applied with treatment group as a treatment effect. The results of ANCOVA model will be summarized as the LSM differences between the study group and the control group, the corresponding 2-sided 95% confidence interval, and p-value.
(Week 8 evaluation will only be applicable to patient receiving treatment 2)

3. Assessment on symptoms of reflux disease using GERD-Q

Descriptive statistics (mean, standard deviation, median, minimum, and maximum) for the changes from baseline in frequency at the first 7 days, 4 weeks, and 8 weeks will be presented by time point. For the changes from baseline in variables measured at the first 7 days, 4 weeks, and 8 weeks after the IP administration, an ANCOVA model including treatment group as treatment effect, and baseline value will be applied. The results of ANCOVA model will be summarized as the least squares mean (LSM) and standard error by treatment group, the LSM differences between the study group and the control group, the corresponding 2-sided 95% confidence interval, and p-value
(Week 8 evaluation will only be applicable to patient receiving treatment 2)

4. Quality of life assessment using GERD-HRQL

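### Time to complete response is followed beyond Week 4 only in unrelieved subjects, so the late Kaplan-Meier curve, and any median that falls there, describes GERD-Q non-responders alone

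*Combined protocol and SAP*

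**What the plan says.** All references are to the combined protocol and SAP.

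- **Event and analysis (9.2.3.2, item 2, and the synopsis).** CR is the first run of 7 consecutive days with symptom score 0, and "the survival time is defined as the time to reach Complete Response (CR) after the first IP administration". Kaplan-Meier plots and medians with 95% confidence intervals are planned by group. For the comparison, "To compare the control group and study group, the log-rank test will be used". No end of follow-up is given.
- **Censoring (9.2.1).** The only text is "For survival analysis, censoring will be utilized".
- **Diary (8.3.14).** The diary is collected at Visit 4. For subjects without relief, "the subject diary will be re-distributed to the subject". Later, "At Visit 5, the subject diary will be collected only from those who have undergone Treatment 2".
- **Relieved subjects (5.1).** "Subjects with symptoms relief at Week 4 measured by GERD-Q Score <8 will have the Safety F/U after 2 weeks" and then leave the study. Section 8.1 makes that contact a telephone visit, and no diary is attached to it.
- **Closing note to item 2 (9.2.3.2).** "Week 8 evaluation will only be applicable to patient receiving treatment 2".
- **Timing (7.2.2 and 8.2).** Dosing starts the day after dispensing. Visit 4 is Day 28 ± 5 and Visit 5 is Day 56 ± 5.

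**The concern.** The GERD-Q result at Visit 4 decides how long a subject is watched for CR. A relieved subject without CR can only be censored at about Day 28, while an unrelieved subject without CR stays at risk to about Day 56. Kaplan-Meier assumes that subjects censored on a given day have the same outlook as those who remain. Here the subjects who leave have just been classed as better, on a questionnaire that counts heartburn and regurgitation days, and those who remain have been classed as worse. The two outcomes should be positively related.

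Faster symptom relief is one of the advantages claimed for the study drug in 1.5 and 1.6, and this endpoint measures it directly. A plot to Day 56 would look like a whole-arm estimate, but after about Day 28 it would describe a small group of non-responders. The size of that group also differs by arm if relief rates differ.

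**Working it through.** **1. The plan's own figure.** Section 9.4.2 assumes relief of 0.885 (control) and 0.94 (study), margin 0.1, one-sided 2.5% and a Z-test with pooled variance. Power = Φ{[(pT − pC + 0.1) − 1.96·√(2p̄(1−p̄)/n)] / √((pC·qC + pT·qT)/n)}. With n = 53 and p̄ = 0.9125 this is Φ{(0.155 − 0.1076)/0.0546} = 0.807, matching the stated 0.80729. Then 53/0.8 = 66.25, rounded up to 67 per arm, or 134 in total. The planning rates can therefore be used below. The documents state no CR rate, event count or power for time to CR.

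**2. Can a subject be relieved without CR?** Yes. In Attachment 2, epigastric pain and nausea are reverse-scored.
- Heartburn on one day and nothing else: 1 + 0 + 3 + 3 + 0 + 0 = 7, which counts as relief.
- Heartburn on 4–7 days, epigastric pain on 2–3 days and nothing else: 3 + 0 + 1 + 3 + 0 + 0 = 7, also relief.

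Neither subject has a 7-day symptom-free run in that week.

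**3. Expected numbers followed beyond Day 28**, n × (1 − relief rate), before removing anyone who already had CR:

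| | Control | Study | Total |
|---|---|---|---|
| 53 per arm | 53 × 0.115 = 6.1 (95% binomial range 2–11) | 53 × 0.06 = 3.2 (0–7) | 9.3 |
| 67 per arm | 67 × 0.115 = 7.7 (3–13) | 67 × 0.06 = 4.0 (1–8) | 11.7 |

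If relief were 80% in both arms, 21 (53 per arm) to 27 (67 per arm) subjects in total would continue. At 70% it would be 32 to 40. The group would then be larger, but still selected on outcome.

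**4. What one late event does.** Suppose 60% of an arm is without CR at Day 28 (assumed). One CR among 6 at risk moves the curve to 0.60 × (1 − 1/6) = 0.50. One CR among 3 moves it to 0.60 × (1 − 1/3) = 0.40. A single subject can set the median.

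**5. Direction and size of bias (illustrative simulation, 200,000 subjects per setting).** CR time was 7 days plus a log-normal time (log SD 1), scaled to give the stated CR by Day 28. Relief was linked to early CR by a latent correlation ρ. Relieved subjects were censored at Day 28 and the others at Day 56. The CR rates and ρ are assumed.

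| Relief | CR by Day 28 | ρ | True CR by Day 56 | Kaplan-Meier CR by Day 56 | Understated by (points) |
|---|---|---|---|---|---|
| 88.5% | 50% | 0 | 0.804 | 0.805 | none |
| 88.5% | 30% | 0.4 | 0.628 | 0.495 | 13.3 |
| 88.5% | 30% | 0.7 | 0.628 | 0.385 | 24.3 |
| 88.5% | 50% | 0.4 | 0.803 | 0.723 | 8.0 |
| 88.5% | 50% | 0.7 | 0.802 | 0.649 | 15.3 |
| 88.5% | 70% | 0.4 | 0.914 | 0.877 | 3.7 |
| 88.5% | 70% | 0.7 | 0.916 | 0.851 | 6.5 |
| 94.0% | 50% | 0.4 | 0.801 | 0.702 | 9.9 |
| 94.0% | 50% | 0.7 | 0.802 | 0.606 | 19.6 |

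In the 30% rows the estimate stays below one half at Day 56, so no median would be reported although more than 60% truly reach CR. With equal true CR of about 0.80 and ρ = 0.7, the two relief rates alone give 0.649 − 0.606 = 0.043, an apparent deficit of 4.3 points for the study arm. A different model of daily symptoms, with relief of 58–87%, understated CR by only about 1 to 5 points. The size is therefore not fixed by the documents.

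**6. The log-rank test.** If CR by Day 28 is 20–80% overall (assumed), 21 to 85 of 106 subjects have their event by then. Later events make up 5–18% of all events if half of the remaining subjects reach CR, and 10–30% if all do. Simulations used 53 per arm, CR by Day 28 of 40% or 60%, ρ of 0.4 or 0.7 and 3,000 runs per setting:
- Equal CR and equal relief (88.5%): the planned test rejected in 4.6–5.0% of runs.
- Equal CR, relief 88.5% v 94.0%: 4.9–5.7%, against 5.3–5.8% when cut at Day 28.
- True 20-point CR difference: power 58–71% as planned and 56–68% when cut at Day 28.

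**The case against.** The strongest reply is that the harm is narrow, and much of that stands.

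- A reader might infer that the log-rank test is invalid or rests on a handful of subjects. That is not supported. Everyone is followed up to the Visit 4 window, most events fall there, and the simulated type I error stays near 5%. Cutting at Day 28 gains nothing for the test and loses a little power.
- A reader might take 6 and 3 as ceilings. They are expected counts under the planning rates, with the ranges shown, and they rise if relief is lower than planned.
- A reader might infer that the median is bound to be wrong. It is affected only if fewer than half of an arm reach CR by about Day 28, and the documents do not say whether that is likely.
- The proportion with CR by Day 56 is not itself a planned estimate. The distortion matters through the plotted tail and a late median, both of which are planned.
- The first-7-day endpoints also measure early speed, and they are unaffected.
- A fixed Day 28 cut would not fully remove the problem. A relieved subject seen on Day 23 has no diary afterwards, while an unrelieved subject seen that day is followed on to Day 28. This is correct, and the fix allows for it.

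The closing Week 8 note does not answer the point. It confirms who has late data but gives no censoring rule for those who do not.

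**Conclusion.** The point holds in this form. Follow-up for CR depends on the Week 4 symptom result, so after about Day 28 the planned curve, and any median falling there, rests on GERD-Q non-responders only. About 6 control and 3 study subjects are expected with 53 per arm, or about 8 and 4 with 67 per arm, before removing earlier CRs. The late curve understates CR if relief and CR are positively related, and is unbiased if they are unrelated. In the simulations shown the shortfall at Day 56 ran from about 1 to 24 points, all under assumed CR rates and correlations. The curve before the Visit 4 window and the primary analysis are not affected. This is a secondary endpoint, but the repair is cheap and should be made before analysis.

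**What to change.** In 9.2.3.2 item 2 and the synopsis, state that the CR Kaplan-Meier plot, median and log-rank test use Treatment 1 diary data only. Every subject without CR, relieved or not, is censored at the earlier of Day 28 of dosing and the last diary day before the Visit 4 collection. A run counts as CR only if its seventh day falls by then. Follow-up then does not depend on the GERD-Q result, even within the ±5 day window.

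Report the median if reached, the Kaplan-Meier proportion with CR by the end of Treatment 1, and numbers at risk. List CR during Treatment 2 descriptively.

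Two other texts need reconciling at the same time. Section 8.4.1.2 has a sentence limiting the secondary endpoints to patients not healed with Treatment 1. Read literally, it would restrict this endpoint to the same 9 to 12 or so subjects. The synopsis classes GERD-Q above 8 as non-healed while relief is below 8, so diary follow-up for a score of exactly 8 is unclear.

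The cost is a short addition to the text and no new data or visits. A few late CR events leave the test, which cost about 0 to 3 points of power in the illustrative simulations. Other assumptions would give a somewhat different loss.
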